13.4. Sample Size Estimation

Ocular discomfort severity, Day 15, ITT: A sample size of 450 in each group will have > 99% power to detect an effect size of [REDACTED] using a 2-group t-test with a [REDACTED] 2-sided significance level.

Ocular discomfort severity, Day 15, Subgroup with [REDACTED] : A sample size of 225 in each group will have 95% power to detect an effect size of [REDACTED] using a 2-group t-test with a [REDACTED] 2-sided significance level.

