7.2. Number of Subjects

Approximately 3200 subjects who are diagnosed with dry eye disease will be screened for this study. Approximately 900 of these subjects will be randomized to either KPI-121 0.25% ophthalmic suspension or vehicle.

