7.3. Treatment Assignment

Subjects will be randomized to 1 of 2 study arms in an approximate 1:1 ratio, allocated at each investigational site. The study arms are: 1) KPI-121 0.25% ophthalmic suspension administered as 1-2 drops in each eye QID for approximately 14 days and 2) vehicle administered as 1-2 drops in each eye QID for approximately 14 days.

Furthermore, subjects will be assigned to a study arm based on the stratification of:

- Ocular discomfort severity scores [REDACTED] (low) and [REDACTED] (high) based on the subject's scoring of ocular discomfort severity [REDACTED] [REDACTED].

The IWRS will assign masked study kit numbers. Bottles of investigational product will be dispensed at designated visits based on the subject's randomization. The Sponsor, Investigators, study staff, and subject will be masked during the randomization process and through the remainder of the study.

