8.3. Subject Withdrawal and Study Termination Criteria

Any subject who wishes to withdraw from the investigational product use or from participation in the study of his or her own accord for any reason is entitled to do so without obligation. The Investigator may also withdraw any subject from the investigational product use or from study participation, if deemed necessary.

Investigational product use may be discontinued and any subject may be discontinued from study participation at any time during the study at the discretion of the Investigator or the Sponsor for any reason including but not limited to:

1. Occurrence of any medical condition or circumstance that exposes the subject to substantial risk and/or does not allow the subject to adhere to the requirements of the protocol.
2. Any SAE, clinically significant AE, severe laboratory abnormality, intercurrent illness, or other medical condition that indicates to the Investigator that continued participation is not in the best interest of the subject.
3. Subject's decision to withdraw.
4. Any woman who becomes pregnant while participating in the study. Information on the pregnancy and outcome will be requested.
5. Subject's failure to comply with protocol requirements or study related procedures.
6. Termination of the study by the Sponsor, FDA, or other regulatory authorities.

In the event study discontinuation of a randomized subject is necessary, the Investigator should make every attempt to have subject complete Visit 4 assessments as possible. The reason for premature discontinuation should be entered onto the eCRF and recorded in the subject chart.

Subjects who withdraw from the study will not be replaced.

Additionally, the trial or parts of the trial may be discontinued by the Sponsor or at the recommendation of the Investigator after consultation with Kala Pharmaceuticals, Inc. This may be based on a significant number of AEs of a similar nature that warrant such action.

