13.5. Level of Significance

[REDACTED] Overall the Type I error rate is controlled at 0.05.

[REDACTED] All other reported *p*-values will be considered descriptive and hypothesis generating.

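### Does the 95% power for the severe-discomfort primary endpoint rest on a subgroup size that the plan does not secure?

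*Combined protocol and SAP*

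**What the plan says.** Section 13.4 sizes two comparisons of ocular discomfort severity (ODS) at Day 15. For the full ITT population: "A sample size of 450 in each group will have > 99% power to detect an effect size of" a redacted value. For the subgroup with more severe baseline discomfort: "A sample size of 225 in each group will have 95% power to detect an effect size of" another redacted value. Both use a two-sided two-group t-test at a redacted level. Section 13.5 adds: "Overall the Type I error rate is controlled at 0.05".

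Section 7.2 sets the total: "Approximately 900 of these subjects will be randomized to either KPI-121 0.25% ophthalmic suspension or vehicle". Section 8.3 says: "Subjects who withdraw from the study will not be replaced". Under Section 7.3, "subjects will be assigned to a study arm based on the stratification of" low or high ODS, with the cut-offs redacted. Section 7.1 leaves further allocation criteria to a data management plan that is not among the documents. Section 13.6 provides for multiple imputation of the primary endpoints under missing at random if more than 5% of data are missing. Section 13.2.2 makes the secondary tests depend on rejecting the primary null hypotheses.

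**The concern.** The two sample sizes use up the whole trial: 450 + 450 = 900, and 225 + 225 = 450 is half of it. Stratified randomization balances the arms within the high-ODS stratum but does not decide how many subjects enter it. Nothing visible states an expected share, a quota or a minimum, and nothing visible is added for subjects without a Day 15 score. Imputation under missing at random keeps such subjects in the analysis but does not restore the information lost.

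The stakes would be real. On the visible wording, secondary testing needs both primary nulls rejected. The chance of reaching it therefore cannot exceed the power of the subgroup test, which is the weaker of the two as stated. A high stratum well below half would lower that ceiling.

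**Working it through.** **Inputs from the documents.** 225 per arm at 95% power and 450 per arm at more than 99% power (Section 13.4); two-sided two-group t-test (Section 13.4); about 900 randomized and about 3200 screened (Section 7.2); overall type I error 0.05 (Section 13.5).

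**Assumptions.** The subgroup's level and effect size are redacted. I take two-sided α from 0.01 to 0.05, subgroup shares s from 30% to 60%, and losses L from 0% to 15%. None of these ranges comes from the documents. Treating a loss as a plain reduction in n is an approximation.

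**Step 1: what effect does the stated figure imply?** With n per arm and standardized effect d,

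power = 1 − F(t₁₋α/2, 2n−2), where F is the noncentral t distribution with 2n − 2 degrees of freedom and noncentrality d√(n/2).

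The 95% cannot be reproduced independently because d is blacked out. Solving for d at n = 225 and power 0.95 gives 0.341 (α = 0.05), 0.350 (0.04), 0.367 (0.025) and 0.399 (0.01). Normal approximation at α = 0.05: (1.960 + 1.645) × √(2/225) = 0.340.

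**Step 2: do the two statements agree?** The same d at 450 per arm gives 99.92% (α = 0.05) to 99.97% (α = 0.01), in line with the stated figure above 99%. The ITT effect size is redacted separately, but at α = 0.05 any d of 0.286 or more would meet it.

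**Step 3: other shares and losses.** n per arm = 450 × s × (1 − L), with d held at its Step 1 value.

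| Share | Loss | n per arm | α = 0.05 | α = 0.025 | α = 0.01 |
|---|---|---|---|---|---|
| 50% | 0% | 225.0 | 95.0% | 95.0% | 95.0% |
| 50% | 5% | 213.8 | 94.0% | 93.9% | 93.8% |
| 50% | 10% | 202.5 | 92.8% | 92.6% | 92.3% |
| 50% | 15% | 191.2 | 91.3% | 91.0% | 90.5% |
| 30% | 0% | 135.0 | 79.6% | 77.7% | 75.3% |
| 40% | 0% | 180.0 | 89.7% | 89.1% | 88.4% |
| 40% | 10% | 162.0 | 86.4% | 85.4% | 84.1% |
| 55% | 0% | 247.5 | 96.6% | 96.7% | 96.8% |
| 55% | 10% | 222.8 | 94.8% | 94.8% | 94.8% |
| 60% | 0% | 270.0 | 97.7% | 97.8% | 98.0% |
| 60% | 10% | 243.0 | 96.3% | 96.4% | 96.5% |

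**Step 4: what share keeps 225 evaluable per arm?** At 5% loss, 450/0.95 = 473.7, so 474 randomized in the stratum (0.50/0.95 = 52.6% of 900). At 10% loss, 450/0.90 = 500 (55.6%). The requirement is thus at least half, rising a little with losses. An uneven split such as 215 and 235 leaves power at 95.0%.

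**Step 5: what would securing the share cost?** Suppose low-stratum entry stopped at 450. If the natural high share were 40%, reaching 450 high-stratum subjects would need 450/0.40 = 1125 eligible subjects. At the planned screening ratio that is 1125 × 3200/900 = 4000 screened. At 30% it is 450/0.30 = 1500 eligible and 1500 × 3200/900 ≈ 5333 screened.

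**The case for a change.** The strongest case for a change is that the subgroup's size is the one design quantity that the total of 900 does not control, and that it bears on a primary endpoint that gates the secondaries. At a 40% share the type II error about doubles, from 5% to between 10.3% and 11.6%. At 30% it is 20% to 25%. Writing the assumed share and loss into Section 13.4 costs nothing.

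The omission is real as far as the visible text goes, and a sentence giving the assumed share would make the section easier to read. The rest is weaker:

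- **Share.** The argument that nothing fixes the stratum's size works in both directions. Nothing visible caps it at half, and a larger stratum gives more than 95%. A cut-off chosen near the middle of the population would make half the natural expectation, but the cut-off is redacted. The sponsor had three completed dry-eye trials to plan from (Section 5).
- **Losses.** Section 13.6 describes a contingency, not a forecast that more than 5% will be missing. Dosing after randomization lasts about two weeks and follows a run-in with a compliance requirement. Rescued subjects stay in the study to Visit 4 (Section 9.2), and Visit 4 assessments are sought from those who stop early (Sections 7.4.6 and 8.3). At a half share, even an assumed 15% loss leaves power above 90%.
- **Absence of a quota.** Its absence from the visible text does not show that none exists. Section 7.1 points to a document that was not supplied, and much of the surrounding text is blacked out.
- **A cap on the low stratum.** This is a trade-off. It could mean hundreds to about two thousand more screenings under the assumed shares. It would also turn away otherwise eligible subjects after a two-week run-in and shift the mix of the ITT population on which the other primary endpoint rests.

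**Conclusion.** No change to the plan follows. Section 13.4 makes a conditional statement that is internally consistent, and the documents do not show that the trial would miss it. Losses alone matter little: about 1 point of power at 5% and 2 to 3 points at 10%, with a half share. The share matters more, but in either direction. Across assumed shares of 40% to 60% and losses of 0% to 10%, power runs from about 84% to 98%.

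Adding the assumed share to Section 13.4 would document a planning assumption. It would not alter the number randomized, the test or the type I error control. The realized stratum size will be known from the randomization system and can be reported with the results.

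This conclusion rests on the effect size being the one implied by the plan's own 95%, on α between 0.01 and 0.05, and on losses acting as a simple reduction in n. The visible text cannot settle whether the true share is near half.

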13.5. Level of Significance

[REDACTED] Overall the Type I error rate is controlled at 0.05.

[REDACTED] All other reported *p*-values will be considered descriptive and hypothesis generating.

13.6. Procedure for Accounting for Missing, Unused or Spurious Data

Any missing, unused, or spurious data will be noted in the final clinical study report. If more than 5% of data are missing, multiple imputation will be employed to analyze incomplete data sets under the assumption that missing data are, at worst, characterized as missing at random (MAR). Imputation will be carried out for the analysis of only the primary endpoints. The reasons for missing data will be recorded and the impact of these reasons and any treatment group imbalance on the assumption of MAR will be evaluated.

13.7. Procedure for Reporting Deviations from the Statistical Plan

Any deviations from the statistical analysis plan will be described and a justification given in the final clinical study report.

14. DIRECT ACCESS TO SOURCE DATA/DOCUMENTS

14.1. Study Monitoring

The progress of the study will be monitored by on-site, written, e-mail, and telephone communications between personnel at the study center and the Sponsor (or designated monitor). The Investigator will allow Kala Pharmaceuticals, Inc. monitors or designee to inspect all CRFs; subject records (source documents); signed informed consent forms; HIPAA authorizations; records of investigational product receipt, storage, and disposition; and regulatory files related to the study.

14.2. Audits and Inspections

Authorized representatives of Kala Pharmaceuticals, Inc, a regulatory authority, an Independent Ethics Committee or an Institutional Review Board may visit the site to perform audits or inspections, including source data verification. The purpose of a Kala Pharmaceuticals, Inc. audit or inspection is to systematically and independently examine all study-related activities and documents to determine whether these activities were conducted, and data were recorded, analyzed, and accurately reported according to the protocol, Good Clinical Practice guidelines of the International Conference on Harmonization, and any applicable regulatory requirements. The investigator should contact Kala Pharmaceuticals, Inc immediately if contacted by a regulatory agency about an inspection.

14.3. Institutional Review Board (IRB)

The Principal Investigator must obtain IRB approval for the investigation. Initial IRB approval, and all materials approved by the IRB for this study including the subject consent form and recruitment materials must be maintained by the Investigator and made available for inspection.

15. QUALITY CONTROL AND QUALITY ASSURANCE

To ensure compliance with Good Clinical Practices and all applicable regulatory requirements, Kala Pharmaceuticals, Inc. may conduct a quality assurance audit. Please see Section 14.2 for more details regarding the audit process.

16. ETHICS

16.1. Ethics Review

This protocol and the informed consent form must be approved by an appropriately constituted and qualified IRB and the approvals made available to the Sponsor or designee prior to the start of enrollment into the study based on these items. Materials used to recruit subjects will be approved by the appropriate IRB and the approvals made available to the Sponsor or designee prior to their use. In addition, the Investigator's Brochure should be submitted to the IRB. Written IRB approval must adequately identify the protocol and informed consent form. Copies of all approved materials, all correspondence with the IRB, and written approval from the IRB must be made available to the Sponsor (or designated monitor).

Any modification of study procedures or amendments to the protocol must be approved by the IRB prior to implementation. In the event that a modification or amendment is considered by the Investigator to be immediately necessary to ensure subject safety, the Investigator will promptly notify his or her IRB and the Sponsor.

Investigators will report all SAEs reported at their site to their IRB, as appropriate.

16.2. Ethical Conduct of the Study

The study will be performed in accordance with ethical principles that have their origin in the Declaration of Helsinki and are consistent with ICH/Good Clinical Practice and applicable regulatory requirements.

16.3. Written Informed Consent

Written informed consent will be obtained from each participant prior to any study-related procedures being performed [prior to or upon Visit 1 (Screening)]. A copy of the signed and dated informed consent document will be given to each subject. The original signed and dated informed consent document must be maintained in the study files at the investigative site and be available for Sponsor or designee review.

Each informed consent will contain Investigator contact information with a telephone number the subject or the subject's authorized representative can call 24 hours a day if they have medical concerns.

17. DATA HANDLING AND RECORDKEEPING

17.1. Inspection of Records

The Investigator will permit trial-related monitoring, audits, IRB review, and regulatory inspection(s) by providing direct access to source data and documents (such as tests performed as a requirement for participation in the study and other medical records required to confirm information contained in the case report form such as medical history) to the monitor.

Electronic case report forms will be used to collect subject data during the course of the trial. Electronic case report forms must be fully completed for each subject and signed by the Investigator upon completion. The Investigator or designated individual shall be responsible for recording trial data on the eCRFs. Access to the eCRFs will be by means of a unique username and password through a secure web-browser. Changes to the original data entries will trigger a reason for change dialogue box while the time, date and user making the change are automatically logged.

The Investigator is required to sign the eCRF on the appropriate page(s) to verify that he/she has reviewed the recorded data. Completed eCRFs will be verified by the Sponsor study monitors or designees at regular intervals during the trial. The Investigator will allow the monitor and other external regulatory body to review and inspect the study files, the eCRFs, subject medical records and other trial related documents as required.

17.2. Retention of Records

The study center will retain all records related to the study in accordance with local and ICH GCP guidelines. Final signed eCRFs will be provided to the site at the end of the study for record retention.

18. PUBLICATION POLICY

The institution and Investigators participating in this trial shall have no right to publish or present the results of this study without the prior written consent of the Sponsor.

20. APPENDICES

APPENDIX 1: SUMMARY OF EVENTS

Procedures	Stage 1		Stage 2	
	Visit 1	Visit 2	Visit 3	Visit 4
	Screening	Randomization	[REDACTED]	End of Study Visit
	14 ± 1 Days Prior to Day 1	Day 1	Day 8 (±1 day)	Day 15 (+2 days)
ICF, HIPAA and Significant Medical History	X			
Subject-rated assessment of ocular discomfort [REDACTED]	X			
Subject-rated assessment of ocular discomfort [REDACTED]		X ^c	X ^c	X ^c
Subject-rated assessment of eye dryness [REDACTED]		X	X	X
Concomitant medication query	X	X	X	X
UPT ^a	X			X
Inclusion/Exclusion	X	X		
AE Assessment	X	X	X	X
assessment of bulbar conjunctival hyperemia	X	X		X
[REDACTED]		X		X
BCVA	X	X		X
Slit lamp biomicroscopy	X	X		X
Corneal fluorescein staining	X	X		X
Unanesthetized Schirmer Test Assessment	X			
IOP measurement	X	X		X
Dilated ophthalmoscopy	X			X
Investigational product administration in-clinic	X ^b	X		
Dispense investigational product	X ^b	X		
[REDACTED]	X ^b	X	X	
Collect investigational product		X ^b		X
[REDACTED]		X	X	X

^aWomen of childbearing potential only; ^bStage 1 Product [REDACTED]

APPENDIX 2: SUBJECT-RATED ASSESSMENT OF EYE DRYNESS

Subjects will be asked to subjectively rate their eye dryness at Visits 2-4. Subjects will be instructed to rate eye dryness using the scales shown below and entered on a source document. The total length of the line from [REDACTED] to [REDACTED] is 100 mm. The length of the line between the [REDACTED] starting point and the first point where the subject's mark crosses the line will be measured and recorded in millimeters. This assessment is a general assessment of both eyes. There will not be a question for each individual eye.

Instantaneous Evaluation of Eye Dryness

Please place a single line across the line below to indicate the severity of your eye dryness [REDACTED]

:
[REDACTED] _____ [REDACTED]

[figure not shown]
APPENDIX 3: SUBJECT-RATED ASSESSMENT OF OCULAR DISCOMFORT⁴

Subjects will be asked to subjectively rate their ocular discomfort severity and frequency during the course of this study. [REDACTED]

[figure not shown]
[REDACTED] This assessment will be collected at Visit 1 (Screening) for eligibility. Further, subjects will be instructed to rate their discomfort [REDACTED] using the scales shown below [REDACTED]. The total length of the lines from [REDACTED] to [REDACTED] and [REDACTED] to [REDACTED] are 100 mm. The length of the line between the [REDACTED] on the severity scale or [REDACTED] on the frequency scale starting point and the first point where the subject's mark crosses the line will be measured and recorded in millimeters. This assessment is a general assessment of both eyes. There will not be a question for each individual eye.

OCULAR DISCOMFORT SEVERITY ASSESSMENT

Please place a single line across the line below to indicate how severe, [REDACTED] you feel your eye discomfort (for example, dryness or irritation) was:

[figure not shown]
**OCULAR DISCOMFORT FREQUENCY ASSESSMENT**

Please place a single line across the line below to indicate how often, [REDACTED] you feel your eye discomfort (for example, dryness or irritation) was:

APPENDIX 4: I [REDACTED] ASSESSMENT OF BULBAR CONJUNCTIVAL HYPEREMIA

[REDACTED] bulbar conjunctival hyperemia at Visits 1, 2, and 4 using the CCLRU Grading Scale.

- (0) None
- (1) Very Slight
- (2) Slight
- (3) Moderate
- (4) Severe

APPENDIX 5: UNANESTHETIZED SCHIRMER TEST EVALUATION

Unanesthetized Schirmer Test evaluation will be conducted at Visit 1 (Screening). Identical Schirmer Test strips will be supplied to each site. When conducting assessments room temperature and humidity should be relatively consistent throughout each visit and throughout the study. Please make certain to allow at least 20 minutes between any corneal staining evaluations and the unanesthetized Schirmer Test.

Unanesthetized Schirmer Test

- While still in the plastic sheath, fold the rounded end of the unanesthetized Schirmer Test strip at the first line on the strip (closest to the rounded end). Additionally, fold a partial second fold at the halfway point of the strip so that the strip does not lie directly in the subject's line of sight.
- Remove the right eye strip from the sheath.
- Ask the subject to look up and gently draw the right lower lid in a downward and temporal direction.
- Place the rounded end of the strip toward the temporal one-third of the lower eyelid.
- Repeat this procedure in the left eye.
- Darken the room, but ensure that the Large E or the ETDRS chart is visible.
- Instruct the subject to relax and look at the chart while blinking normally or have subject gently close eyes.
- Strips are removed after 5 minutes.
- After removing the strips, with a pen draw a horizontal line across the leading edge of moisture and a second horizontal line across the lowest point of moisture.
- Using a ruler and/or the millimeters recorded on the strips, measure a point halfway between the 2 lines and record this as the amount of wetting.
- Retain Schirmer strips in source documentation.

APPENDIX 6: BEST-CORRECTED VISUAL ACUITY

BCVA will be conducted at Visits 1, 2, and 4.

Visual acuity testing should precede any examination requiring contact with the eye or instillation of study dyes. LogMAR visual acuity must be assessed using an ETDRS or modified ETDRS chart. Visual acuity testing should be performed with best correction using subject's own corrective lenses (spectacles only) or pinhole refraction.

An ETDRS or modified ETDRS chart may be used. If a Lighthouse chart is used (24.5" by 25"; either reflectance or retro-illuminated), the subject must view the chart from a distance of exactly 4 meters (13.1 feet). If smaller reproductions (18" by 18", e.g., Prevent Blindness) are used, the subject viewing distance should be exactly 10 feet. Reflectance wall charts should be frontally illuminated (60-watt bulb or a well-lit room).

The subject should be positioned according to the elevation of the chart (either seated or standing) so that the chart is at a comfortable viewing angle. The right eye should be tested first. The subject should attempt to read each letter, line-by-line, left to right, beginning with line 1 at the top of the chart. The subject should be told that the chart has letters only, no numbers. If the subject reads a number, he or she should be reminded that the chart contains no numbers, and the examiner should then request a letter instead of the number. The subject should be asked to read slowly, about 1 letter per second, to achieve the best identification of each letter. He/she is not to proceed to the next letter until he/she has given a definite response. If the subject changes a response before he has read aloud the next letter, then the change must be accepted.

Maximum effort should be made to identify each letter on the chart encouraging the subject to guess. When it becomes evident that no further meaningful readings can be made, the examiner should stop the test. The number of letters missed or read incorrectly should be noted.

In order to provide standardized and well-controlled assessments of visual acuity during the study, consistently use the same lighting conditions during the entire study.

Calculations: logMAR VA = Baseline value + (n X 0.02)

where: the baseline value is the logMAR number of the last line read (at least 1 letter read correctly in this line), and

“n” is the total number of letters missed up to and including the last line read, and

“0.02” is the value for each letter

